7.3 Baseline Disease Evaluation

For the full analysis set and safety analysis set, each variable at baseline will be calculated.

Table 7.3-1 Baseline Pathologic Evaluation		
Variable	Method	Level
Cardiothoracic ratio (%)	Descriptive statistics	-
NYHA classification	Distribution	Class I, Class II, Class III, Class IV
Severity of lower limb edema	Distribution	None, Mild, Moderate, Severe
Pulmonary congestion	Distribution	None, Mild, Moderate, Severe
Presence of jugular venous distension	Distribution	Yes, No
Jugular venous distension (cm)	Descriptive statistics	-
Presence of jugular venous distension (baseline value)	Distribution	Yes, No
Jugular venous distension (cm) (subjects with baseline value)	Descriptive statistics	-
Presence of hepatomegaly	Distribution	Yes, No
Hepatomegaly (cm)	Descriptive statistics	-
Presence of hepatomegaly (baseline value)	Distribution	Yes, No
Hepatomegaly (cm) (subjects with baseline value)	Descriptive statistics	-
Pulmonary rales	Distribution	Yes, No
Third cardiac sound	Distribution	Yes, No
Daily urine volume	Distribution	<1500 mL, ≥1500 mL
Creatinine	Distribution	<2 mg/dL, ≥2 mg/dL
Plasma AVP concentration	Distribution	≤3.1 pg/mL, >3.1 pg/mL
Albumin	Distribution	<3 g/dL, ≥3 g/dL

7.4 Treatment Compliance

Treatment compliance will be summarized for the full analysis set. Distributions for presence or absence of day of discontinuation during IMP (injection) administration will be calculated. Distributions for presence or absence of days of incomplete IMP (injection) administration as well as days of deviant duration of IMP administration from the start time to the end time (outside the acceptable range of 55 to 65 minutes) will be calculated. Distributions for days of missing an IMP (tablet) dose will also be calculated.

7.5 Prior and Concomitant Medications

For the full analysis set and safety analysis set, distributions for usage of concomitant medication on the initial IMP administration day will be calculated.

Table 7.5-1 Usage of Concomitant Medication on Initial IMP Administration Day	
Variable	Level
Use of loop diuretic	Monotherapy with loop diuretic, Loop diuretic + other diuretic
Dose of loop diuretic (Furosemide equivalent*)	<40 mg/day, ≥40 mg/day and <80 mg/day, ≥80 mg/day
Category of diuretic *Concomitant use of diuretic drugs other than loop diuretic, thiazide diuretic, and anti-aldosterone drug is not summarized.	Monotherapy with loop diuretic, Loop diuretic + thiazide diuretic, Loop diuretic + anti-aldosterone drug, Loop diuretic + thiazide diuretic + anti-aldosterone drug
Thiazide diuretic	Yes, No
Anti-aldosterone drug	Yes, No
Drugs for heart failure other than diuretics	Yes, No
Digitalis product	Yes, No
ACE inhibitor	Yes, No
Beta blocker	Yes, No
Angiotensin receptor blocker	Yes, No

*Furosemide equivalent dose of 40 mg is defined as bumetanide, 1 mg; piretanide, 6 mg; azosemide, 60 mg; and torasemide, 8mg

7.6 Protocol Deviations

For randomized subjects, distributions for presence or absence of deviations in each CRF classification (Dosing, Inclusion/Exclusion Criteria, Met Withdrawal Criteria But Was

Not Withdrawn, Prohibited Concomitant Medications) will be calculated. Distributions of subjects with at least one deviation will also be calculated.

8 Efficacy Analysis

The following analyses will be performed in the full analysis set.

8.1 Primary Efficacy Endpoint

The primary endpoint is the change in body weight from baseline (before IMP administration on Day 1) at time of final IMP administration (day after final IMP administration), and the non-inferiority of OPC-61815 16-mg injection to tolvaptan 15-mg tablet in the change from baseline in body weight will be confirmed with a noninferiority margin of 0.48.

8.1.1 Primary Efficacy Analysis

Main analysis is an analysis of the primary endpoint using an ANCOVA model with treatment as a fixed effect factor and baseline body weight as a covariate. The least square mean difference and its two-sided 95% CI (based on the t distribution) between the OPC-61815 16-mg injection group and the tolvaptan 15-mg tablet group will be calculated. The non-inferiority of OPC-61815 16-mg injection to tolvaptan 15-mg tablet will be confirmed when the upper limit of the CI does not exceed 0.48.

At each time point, the measured values, changes, and percent changes in body weight from baseline will be summarized by treatment group using descriptive statistics.

Using the main analysis model excluding baseline body weight, the least-square mean of the difference between the OPC-61815 16-mg injection group and the tolvaptan 15-mg group and its two-sided 95% CI will also be calculated.

For changes in body weight from baseline, a timecourse (mean \pm SD) from Day 1 of treatment period to follow-up will be created for each treatment group.

8.1.2 Sensitivity Analyses

No sensitivity analysis will be performed in this trial.

8.1.3 Technical Computational Details for Primary Efficacy Analysis

SAS code is shown below.

```
proc glm data=DATA;  
  class TRTP;  
  model CHG= TRTP BASE;
```

```
lsmeans TRTP / cl pdiff=control('CONTROL');
run;
```

8.2 Key Secondary Efficacy Endpoint

Key secondary endpoints are not set.

8.3 Secondary Efficacy Analyses

8.3.1 Lower Limb Edema and Pulmonary Congestion

For lower limb edema and pulmonary congestion, the improvement rate and the resolution rate at the time of final IMP administration will be determined in each group, and the differences and their two-sided 95% CIs (exact) in the rates between the OPC-61815 16-mg injection group and the tolvaptan 15-mg tablet group will be calculated. The improvement rate is defined as the proportion of subjects in whom the symptom is present at baseline and it markedly improved or improved after IMP administration (for the improvement category, see [Table 8.3.1-1](#)). The resolution rate is defined as the proportion of subjects in whom the symptom is present at baseline and it resolved after IMP administration. For lower limb edema, the improvement rate will be calculated for each treatment group at each time point and the time course will be plotted.

Shift tables for the severity of the symptoms from baseline at the time of final IMP administration and each time point by treatment group will be prepared.

Table 8.3.1-1 Improvement Category of Lower Limb Edema and Pulmonary Congestion		
	Improvement category	Assessment criteria
1	Markedly improved	The symptom resolved or improved by ≥ 2 categories.
2	Improved	The symptom improved by 1 category. (Symptom resolution will be categorized as “markedly improved.”)
3	Unchanged	The symptom remained unchanged or was absent throughout the trial period.
4	Deteriorated	The symptom worsened by ≥ 1 category.

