7.4.2 Secondary Endpoint Analysis

7.4.2.1 Lower Limb Edema and Pulmonary Congestion

For lower limb edema and pulmonary congestion, the improvement rate and the resolution rate at the time of final IMP administration will be determined in each group, and the differences and their two-sided 95% CIs in the rates between the OPC-61815 16-mg injection group and the tolvaptan 15-mg tablet group will be calculated. The improvement rate is defined as the proportion of subjects in whom the symptom is present at baseline and it markedly improved or improved after IMP administration (for the improvement category, see [Table 7.4.2.1-1](#)). The resolution rate is defined as the proportion of subjects in whom the symptom is present at baseline and it resolved after IMP administration.

Shift tables for the severity of the symptoms from baseline at the time of final IMP administration and each time point by treatment group will be prepared.

Table 7.4.2.1-1 Improvement Category of Lower Limb Edema and Pulmonary Congestion		
	Improvement category	Assessment criteria
1	Markedly improved	The symptom resolved or improved by ≥ 2 categories.
2	Improved	The symptom improved by 1 category. (Symptom resolution will be categorized as “markedly improved.”)
3	Unchanged	The symptom remained unchanged or was absent throughout the trial period.
4	Deteriorated	The symptom worsened by ≥ 1 category.

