8.3.4 NYHA Classification

A shift table for the NYHA classification from baseline at the time of final IMP administration and each timepoint by treatment group will be prepared.

For Class II and higher subjects, the proportion of those who have improved from baseline by 1 or more NYHA class at the time of final IMP administration will be calculated for each treatment group to determine the difference between the OPC-61815 16 mg injection group and the tolvaptan 15 mg tablet group and its two-sided 95% CI (exact).

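### Lower limb edema, pulmonary congestion and NYHA class are graded on four levels but compared between arms, with a CI, only as unadjusted yes/no rates, which costs some precision

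*SAP*

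**What the plan says.** - **Scales.** Protocol 3.7.2.2 and 3.7.2.3 grade lower limb edema and pulmonary congestion from 0 to 3, and 3.7.2.4 gives four NYHA classes. SAP 7.3 tabulates the same levels at baseline: "None, Mild, Moderate, Severe" and "Class I, Class II, Class III, Class IV".
- **Edema and pulmonary congestion.** SAP 8.3.1 states that "the improvement rate and the resolution rate at the time of final IMP administration will be determined in each group", and plans "the differences and their two-sided 95% CIs (exact) in the rates", for improvement and for resolution. Protocol 7.4.2.1 defines the first: "The improvement rate is defined as the proportion of subjects in whom the symptom is present at baseline and it markedly improved or improved". I read both rates as being taken among subjects who have the sign at baseline.
- **NYHA.** Protocol 7.4.2.4 plans a shift table only. SAP 8.3.4 adds a rate difference with an exact CI in subjects of Class II or higher, based on "the proportion of those who have improved from baseline by 1 or more NYHA class".
- **Full scale.** It appears only descriptively: "Shift tables for the severity of the symptoms from baseline at the time of final IMP administration" and at each time point, with a similar table for NYHA. These tables carry no treatment difference and no CI.
- **Other signs.** SAP 8.3.2 compares jugular venous distension, hepatomegaly and cardiothoracic ratio as measured changes by ANCOVA with a 95% CI.
- **Status.** SAP 8.2 sets no key secondary endpoint. No margin, effect size or power is given for any secondary endpoint.

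**The concern.** SAP Table 8.3.1-1 separates four outcomes: markedly improved, improved, unchanged and deteriorated. No interval uses all four. The improvement rate pools the first two and also pools the last two. The resolution rate pools everything short of complete disappearance. Among subjects with the sign at baseline, none of the planned rates can tell a subject who worsened from one who stayed the same, and that is a distinction one wants to see in a non-inferiority trial. For subjects who start at mild, improved and resolved are the same event, so the two rates partly repeat each other. Baseline grade strongly limits what change is possible, yet it is not used.

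The secondary objective is a comparison with the tablet, and the primary endpoint is body weight. These signs and the NYHA class are part of the clinical support for similar decongestion. Intervals wider than the data require make that support less informative in either direction.

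**Working it through.** **The plan's own figure.** The only sample size stated is for body weight. With margin 0.48, SD 1.25, true difference 0, two-sided 5% and 90% power, n per arm = 2 × (1.960 + 1.282)² × 1.25² / 0.48² = 142.5, so 143. With the t distribution, power is 89.9% at 143 and 90.1% at 144, so 288 is reproduced. The calculation assumes equal arms. It has no counterpart for the graded endpoints, so everything below rests on assumptions.

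**1. Precision with equal arms.** Under proportional odds, the information on the log odds ratio from N subjects (1:1) is N/12 × (1 − Σp³) for the full scale and N/4 × P(1 − P) for a cut with cumulative proportion P. The relative efficiency of the cut is therefore 3P(1 − P) / (1 − Σp³).

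| Assumed distribution, best to worst | Cut | Efficiency |
|---|---|---|
| Change category 35/25/35/5% | improved, P = 0.60 | 0.72/0.8985 = 0.80 |
| Change category 45/20/30/5% | improved, P = 0.65 | 0.6825/0.8737 = 0.78 |
| Change category 20/30/45/5% | improved, P = 0.50 | 0.75/0.8737 = 0.86 |
| Final grade 25/25/25/25% | resolved, P = 0.25 | 0.5625/0.9375 = 0.60 |
| Final grade 60/30/8/2% | resolved, P = 0.60 | 0.72/0.7565 = 0.95 |
| NYHA change 5/35/55/5% | at least one class, P = 0.40 | 0.91 |

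On the log odds scale, the interval from the cut is wider by 1/√efficiency: from 1/√0.95 = 1.03 to 1/√0.60 = 1.29 times. This is before any baseline adjustment. For scale, the approximate 95% half-width of a rate difference, 1.96 × √(2P(1 − P)/n), is about 11 to 16 percentage points for 144 down to 72 affected subjects per arm.

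**2. Edema, assumed odds ratio 2.0.** Inputs, none of them from the documents:
- 100 or 130 affected subjects per arm.
- Baseline mild/moderate/severe 65/28/7, 50/35/15 or 30/45/25%.
- Two tablet-arm tables of final grade 0/1/2/3. Table 1: mild .45/.50/.04/.01, moderate .20/.40/.37/.03, severe .10/.25/.40/.25. Table 2: mild .30/.63/.06/.01, moderate .10/.35/.50/.05, severe .05/.15/.35/.45.

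This gives 3 × 2 × 2 = 12 scenarios.

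Worked case (table 1, mix 50/35/15, 130 per arm):
- Tablet improvement rate: 0.50 × 0.45 + 0.35 × 0.60 + 0.15 × 0.75 = 0.548. Doubling the odds within each baseline grade gives 0.50 × 0.621 + 0.35 × 0.75 + 0.15 × 0.857 = 0.701.
- SE = √[(0.548 × 0.452 + 0.701 × 0.299)/130] = 0.059, so z = 0.154/0.059 ≈ 2.6 and power is about 73 to 74%. The simulation gave 73%.
- Resolution: 0.310 against 0.454, SE 0.060, z ≈ 2.4. The simulation gave 67%.
- Full scale: a rank test stratified by baseline grade had 83% power, and an ANCOVA of final grade on treatment and baseline grade 81%.
- Loss against the stratified rank test: 83 − 73 = 10 points for improvement and 83 − 67 = 16 for resolution.

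Across the 12 scenarios, with large-sample methods on both sides, the loss is about 3 to 14 points for improvement and 10 to 31 for resolution. Simulation error is a point or two at each end. The improvement-rate loss is smallest when most subjects are mild at baseline.

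**3. NYHA, separate assumption.** Tablet-arm change by two or more classes / one / none / worse of 5/35/55/5%, 100 per arm, odds ratio 2.13. The injection arm becomes 10.1/48.6/38.9/2.4%.
- Full scale: information 200/12 × (1 − 0.177) = 13.7. Power = Φ(0.756 × √13.7 − 1.96) = 80%.
- Planned cut: 0.400 against 0.587. Power = Φ[(0.187 − 1.96 × 0.0707)/0.0695] = 76%.
- Loss: about 4 points. With 72 to 144 per arm it is 4 to 5.

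Pulmonary congestion was not simulated separately.

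**The case against.** **Power is an awkward yardstick.** These endpoints have no test or margin. The trial is planned for equal arms, at a dose chosen for similar exposure, and nothing in the documents supports an odds ratio of 2.0. This stands. The power figures only illustrate lost precision. Step 1, which needs no treatment effect, shows the same direction.

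**The loss can easily be overstated.** A reader might infer that dichotomising costs some 8 to 19 points for all three endpoints, by setting an exact test on the unadjusted improvement rate against a large-sample, baseline-stratified test. The documents do not support that. It mixes three things: exactness, baseline adjustment and the cut itself. In the worked case exactness alone lowers the improvement rate from 73% to 68%. It also covers edema only. An unadjusted rank test on grade change gains only about 2 to 9 points over the improvement rate, and under 5 in 10 of the 12 scenarios. Much of the benefit therefore comes from using baseline grade.

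**The simulation suits the remedy.** Data were generated with a common odds ratio, and the proportional-odds model itself was not run. Stratified rank and ANCOVA analyses stood in for it. This also stands. Eligibility needs only one of three congestive signs, so the pulmonary congestion subset may be small and its grades sparse.

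**Information is not thrown away.** The two cuts are reported together, and each recovers part of what the other hides. Shift tables keep the full scale, and three other signs are compared as measurements. The cuts are natural, prespecified and easy to read, and leaving out baseline adjustment does not bias a randomised comparison. All true. What remains is that no interval uses the full grading, and neither document says why these graded signs are handled differently from those in SAP 8.3.2.

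**Conclusion.** The point holds as a low-cost improvement. The only between-arm estimates with a CI for edema, pulmonary congestion and NYHA are unadjusted yes/no rate differences. They merge worsening with no change and make no use of baseline severity.

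The size depends on distributions that the documents do not give. The edema and NYHA losses in the working hold only under the odds ratios and subset sizes stated there, and no general figure should be quoted for all three endpoints. With equal arms, the cuts alone widen intervals on the log odds scale by roughly 3% to 29% under the distributions tried.

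A reader might go further and infer that the secondary analyses are invalid or that the non-inferiority conclusion is at risk. Neither follows. The rates are legitimate estimates, the shift tables preserve the data, and the primary analysis of body weight does not depend on them.

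**What to change.** Keep the rates, their exact CIs and the shift tables. Add to SAP 8.3.1 and 8.3.4 one full-scale between-arm estimate per endpoint:

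- **Population:** FAS subjects with the sign present at baseline (NYHA Class II or higher).
- **Model:** proportional odds for the grade at the final administration time point, with treatment as factor and baseline grade as covariate. Report the common odds ratio with a two-sided 95% CI.
- **Fallback:** where grades are sparse or proportional odds is doubtful, an ANCOVA of the final grade on treatment and baseline grade, giving a mean difference with a 95% CI. State in advance which applies when. The covariate should be the baseline grade, not baseline body weight as in SAP 8.3.2.

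New onset in subjects free of the sign at baseline would still be seen only in the shift tables.

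The cost is a short SAP edit and three extra outputs on data already collected. No testing hierarchy is disturbed, and SAP 8.3.4 already goes beyond the protocol by adding an NYHA comparison. The downside is an effect measure less familiar to clinicians than a rate difference, which is why the rates stay alongside it.

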8.3.2 Jugular Venous Distension, Hepatomegaly, and Cardiotoracic Ratio

The changes in jugular venous distension, hepatomegaly, and cardiotoracic ratio from baseline at time of final IMP administration will be analyzed using an ANCOVA model with treatment as a fixed effect factor and baseline body weight as a covariate, and the least-square mean differences and their two-sided 95% CIs (based on the t distribution) between the OPC-61815 16- mg injection group and the tolvaptan 15-mg tablet group

will be calculated. In addition, at each time point, measured values and changes from baseline will be summarized by treatment group using descriptive statistics. For jugular venous distension and hepatomegaly, the time course of changes from baseline to each time point will be plotted (mean \pm SD). Note that the absence of jugular venous distension and hepatomegaly will be indicated as 0 cm. The above data on jugular venous distension and hepatomegaly will also be summarized for subjects with baseline value and the time course will be plotted in the same manner. For the presence/absence of jugular venous distension and hepatomegaly, shift tables in changes from baseline at the final IMP administration and at each timepoint following IMP administration will be prepared by each treatment group.

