6.3 Pharmacodynamics

A pharmacodynamic analysis will be conducted on the pharmacodynamic analysis set (see [Section 7.2](#)).

For the following endpoints, measured values and changes from baseline at each time point will be summarized by treatment group using descriptive statistics (n, mean, SD, minimum, median, and maximum). For changes from baseline in daily urine volume, daily fluid intake, and daily fluid valance after IMP administration on Day 1 and after IMP administration on Day 5, the mean difference ([OPC-61815 16-mg injection group] – [tolvaptan 15-mg tablet group]) and its 95% CI will be calculated.

- Daily urine volume
- Daily fluid intake

- Daily fluid balance
- Serum sodium concentration and sodium potassium concentration
- Serum osmolality
- Biomarkers (plasma AVP concentration, plasma BNP concentration, plasma renin activity, serum NT-proBNP concentration, and serum troponin I concentration)
- Daily urine sodium excretion
- Daily urine potassium excretion
- Urine osmolality

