7.4.2.2 Jugular Venous Distension, Hepatomegaly, and Cardiotoracic Ratio

The changes in jugular venous distension, hepatomegaly, and cardiotoracic ratio from baseline at time of final IMP administration will be analyzed using an ANCOVA model with treatment as a fixed effect factor and baseline body weight as a covariate, and the least-square mean differences and their two-sided 95% CIs between the OPC-61815 16-mg injection group and the tolvaptan 15-mg tablet group will be calculated. In addition, at each time point, measured values and changes from baseline will be summarized by treatment group using descriptive statistics. For the presence of jugular venous distension

and hepatomegaly, shift tables in changes from baseline at the final IMP administration and at each timepoint following IMP administration will be prepared by each treatment group.

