10.4 Statistical Analyses

The plasma drug concentration data will be summarized using descriptive statistics as follows:

- At each time point, the plasma drug concentration data will be summarized by compound and by treatment group using descriptive statistics.
- The descriptive statistics to be calculated include number of subjects (n), mean, SD, coefficient of variation, minimum, median, and maximum.

11 Pharmacodynamic Analyses

A pharmacodynamic analysis will be conducted on the pharmacodynamic analysis set.

For the following endpoints, measured values and changes from baseline at each time point will be summarized by treatment group using descriptive statistics (n, mean, SD, minimum, median, and maximum). For changes from baseline in daily urine volume, daily fluid intake, and daily fluid balance after IMP administration on Day 1 and after IMP administration on Day 5, the mean difference ([OPC-61815 16-mg injection group] – [tolvaptan 15-mg tablet group]) and its 95% CI (based on the t distribution) will be calculated. For daily urine volume after IMP administration, the mean changes from baseline after IMP administration on Day 1 and after IMP administration on Day 5 and their two-sided 95% CIs (based on the t-distribution) will be calculated.

For daily urine volume, a transition chart of measurements (mean \pm SD) from the run-in period to Day 5 will be created in each group. For changes from baseline after IMP administration on Day 1 and after IMP administration on Day 5, a bar graph of the mean (two-sided 95% CI) with the horizontal axis representing treatment groups will also be created.

- Daily urine volume
- Daily fluid intake
- Daily fluid balance
- Serum sodium concentration, serum potassium concentration
- Serum osmolality
- Biomarkers (plasma arginine vasopressin [AVP] concentration, plasma brain natriuretic peptide [BNP] concentration, plasma renin activity, serum NT-proBNP concentration, and serum troponin I concentration)
- Daily urine sodium excretion
- Daily urine potassium excretion
- Urine osmolality

12 Pharmacogenomic Analyses

No pharmacogenomic analysis will be performed in this trial.

13 Interim Analysis

No interim analysis will be performed in this trial.

14 Changes in the Planned Analyses

None.

15 References

None.

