Appendix 1**List of Summary Tables**

CT-1 Subject Disposition (Screened Subjects)

CT-2.1 Reasons for Discontinuation (Randomized Subjects)

CT-2.2 Protocol Deviations (Randomized Subjects)

CT-3.1.1 Demographic and Baseline Characteristics (Full Analysis Set)

CT-3.1.2 Demographic and Baseline Characteristics (Safety Analysis Set)

CT-3.2.1 Underlying Disease Leading to Heart Failure (Full Analysis Set)

CT-3.2.2 Underlying Disease Leading to Heart Failure (Safety Analysis Set)

CT-3.2.3 Medical History (Full Analysis Set)

CT-3.2.4 Medical History (Safety Analysis Set)

CT-3.3.1 Concomitant Medications Used on the First Day of Trial Drug Administration (Full Analysis Set)

CT-3.3.2 Concomitant Medications Used on the First Day of Trial Drug Administration (Safety Analysis Set)

CT-3.4.1 Baseline Disease Evaluation (Full Analysis Set)

CT-3.4.2 Baseline Disease Evaluation (Safety Analysis Set)

CT-5.1 Analysis of Covariance for Change from Baseline in Body Weight at the time of Day After Final IMP Administration (Full Analysis Set)

CT-5.2 Descriptive Statistics for Change from Baseline in Body Weight (Full Analysis Set)

CT-5.3 Descriptive Statistics for Change Rate from Baseline in Body Weight (Full Analysis Set)

CT-5.4 Treatment Difference for Change From Baseline in Body Weight at the time of Day After Final IMP Administration (Full Analysis Set)

CT-5.5 Subgroup Analysis for Change from Baseline in Body Weight at the time of Day After Final IMP Administration (Full Analysis Set)

CT-6.1.1 Improvement Rate for Lower Limb Edema and Pulmonary Congestion at the time of Day After Final IMP Administration (Full Analysis Set)

CT-6.1.2 Improvement Rate for Lower Limb Edema (Full Analysis Set)

- CT-6.2 Disappearance Rate for Lower Limb Edema and Pulmonary Congestion at the time of Day After Final IMP Administration (Full Analysis Set)
- CT-6.3 Shift Table for Lower Limb Edema (Full Analysis Set)
- CT-6.4 Shift Table for Pulmonary Congestion (Full Analysis Set)
- CT-6.5.1 Analysis of Covariance for Change from Baseline in Jugular Venous Distension at the time of Day After Final IMP Administration (Full Analysis Set)
- CT-6.5.2 Analysis of Covariance for Change from Baseline in Jugular Venous Distension at the time of Day After Final IMP Administration (Subjects With Baseline Value in Full Analysis Set)
- CT-6.6.1 Analysis of Covariance for Change from Baseline in Hepatomegaly at the time of Day After Final IMP Administration (Full Analysis Set)

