- CT-6.6.2 Analysis of Covariance for Change from Baseline in Hepatomegaly at the time of Day After Final IMP Administration (Subjects With Baseline Value in Full Analysis Set)
- CT-6.7 Analysis of Covariance for Change from Baseline in Cardiothoracic Ratio at the time of Day After Final IMP Administration (Full Analysis Set)
- CT-6.8.1 Descriptive Statistics for Jugular Venous Distension (cm) (Full Analysis Set)
- CT-6.8.2 Descriptive Statistics for Jugular Venous Distension (cm) (Subjects With Baseline Value in Full Analysis Set)
- CT-6.9.1 Descriptive Statistics for Hepatomegaly (cm) (Full Analysis Set)
- CT-6.9.2 Descriptive Statistics for Hepatomegaly (cm) (Subjects With Baseline Value in Full Analysis Set)
- CT-6.10 Descriptive Statistics for Cardiothoracic Ratio (%) (Full Analysis Set)
- CT-6.11 Shift Table for Jugular Venous Distension (Full Analysis Set)
- CT-6.12 Shift Table for Hepatomegaly (Full Analysis Set)
- CT-6.13 Disappearance Rate for Pulmonary rales and Third Cardiac Sound at the time of Day After Final IMP Administration (Full Analysis Set)
- CT-6.14 Shift Table for Pulmonary rales (Full Analysis Set)
- CT-6.15 Shift Table for Third Cardiac Sound (Full Analysis Set)

CT-6.16 Improvement Rate for NYHA Classification at the time of Day After Final IMP Administration (Full Analysis Set)

CT-6.17 Shift Table for NYHA Classification (Full Analysis Set)

CT-7.1 Extent of Exposure to Investigational Medicinal Product (Safety Analysis Set)

CT-7.2 Treatment Compliance (Full Analysis Set)

CT-8.1 Overall Summary of Adverse Events (Safety Analysis Set)

CT-8.2 Incidence of Treatment-emergent Adverse Events by MedDRA System Organ Class and Preferred Term (Safety Analysis Set)

CT-8.3 Incidence of Drug-related Treatment-emergent Adverse Events by MedDRA System Organ Class and Preferred Term (Safety Analysis Set)

CT-8.4 Incidence of Treatment-emergent Adverse Events by Severity by MedDRA System Organ Class and Preferred Term (Safety Analysis Set)

CT-8.5 Incidence of Drug-related Treatment-emergent Adverse Events by Severity by MedDRA System Organ Class and Preferred Term (Safety Analysis Set)

CT-8.6 Incidence of Treatment-emergent Adverse Events Occurring in 2% or More of Subjects in Any Treatment Group by MedDRA System Organ Class and Preferred Term (Safety Analysis Set)

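### The secondary ANCOVAs adjust for body weight instead of each variable's own baseline, and the urine and fluid comparisons adjust for nothing; adding the own baseline gains precision for one degree of freedom.

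*SAP*

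**What the plan says.** For the primary endpoint, baseline body weight is the outcome's own baseline. SAP 8.1.3 shows this in the code: "model CHG= TRTP BASE".

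For three secondary variables the same covariate is kept. Under SAP 8.3.2, changes in jugular venous distension (cm), hepatomegaly (cm) and cardiothoracic ratio (%) "will be analyzed using an ANCOVA model with treatment as a fixed effect factor and baseline body weight as a covariate". Protocol 7.4.2.2 specifies the same model, "with treatment as a fixed effect factor and baseline body weight as a covariate". SAP 8.3.2 also codes an absent jugular distension or hepatomegaly as 0 cm. It plans a second analysis restricted to subjects with a baseline value, listed in SAP Appendix 1 as CT-6.5.2 and CT-6.6.2, with no further covariate named.

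For the pharmacodynamic variables, SAP 11 begins "For changes from baseline in daily urine volume, daily fluid intake, and daily fluid balance" and gives only a mean difference with a t-based 95% CI after the Day 1 and Day 5 doses. Protocol 6.3 has the same plan.

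SAP 3.4 defines a baseline for each variable: the last run-in measurement for the congestive signs, the run-in value for cardiothoracic ratio, and the 24 hours before the first dose for urine and fluid.

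**The concern.** Baseline body weight is a natural covariate for change in body weight. There is no stated reason why it should be the sole covariate for a venous height, a liver width or a chest x-ray ratio. The usual strong predictor of a change score is the variable's own starting value, and here that value is either replaced by body weight or only subtracted.

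The case is clearest for jugular distension and hepatomegaly. With absence coded 0 cm, a subject who starts at 0 cannot fall and one who starts at x cm can fall by at most x, so change is bounded by the own baseline. Restricting to subjects with a baseline value removes those at the floor, but the bound still differs between the remaining subjects.

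At stake is the precision of the supportive comparisons between injection and tablet, which are reported as estimates with intervals. The primary conclusion is not at stake: for the secondary variables SAP 8.2 states "Key secondary endpoints are not set", and no margin or test uses them.

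**Working it through.** **The plan's own figure.** The only computed figure is the primary sample size. With margin 0.48, SD 1.25, true difference 0, one-sided 2.5% and 90% power, the normal approximation gives 2 × (1.960 + 1.282)² × 1.25² / 0.48² = 142.5, so 143 per group. The non-central t gives 144 per group (power 90.1%), matching the stated 288. This point does not touch it. The plan gives no figure for the secondary models.

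**Inputs.** 144 per group, 1:1 (protocol 3.6.1 and 7.1). The correlation ρ between baseline and final value and the ratio k = SD(final)/SD(baseline) are not in the documents. All values of ρ and k below are assumptions.

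**Formula.** In units of the baseline variance, the variance of the change is 1 + k² − 2ρk, and the residual variance after adjusting for the own baseline is k²(1 − ρ²). Hence

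SE ratio = √[k²(1 − ρ²) / (1 + k² − 2ρk)].

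The denominator minus the numerator equals (1 − ρk)², which is never negative. Adjustment therefore cannot raise the large-sample variance, and the gain vanishes only when ρk = 1.

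**Results: SE of own-baseline ANCOVA / SE of change analysis**

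| k | ρ = 0.3 | ρ = 0.5 | ρ = 0.7 |
|---|---|---|---|
| 0.7 | 0.646 | 0.682 | 0.700 |
| 0.85 | 0.736 | 0.788 | 0.832 |
| 1 | 0.806 | 0.866 | 0.922 |
| 1.5 | 0.933 | 0.982 | 0.999 |
| 2 | 0.979 | 1.000 | 0.963 |

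At k = 1 and ρ = 0.9 or 0.95 the ratio is 0.975 or 0.987. One entry in full: at k = 0.7, ρ = 0.3, √[0.49 × 0.91 / (1.49 − 0.42)] = √0.417 = 0.646.

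**Does body weight already do the job?** The formula takes body weight as unrelated to the change. In a simulation (4,000 runs, 144 per arm, bivariate normal), the body-weight covariate altered the SE of the change analysis by a factor of only 0.99-1.00. The ratio of own-baseline SE to body-weight SE was 0.807, 0.867 and 0.914 at k = 1 and ρ = 0.3, 0.5 and 0.7, close to the table. With body weight correlated 0.3 with the own baseline (k = 1, ρ = 0.5) it was 0.881. Every mean estimate lay within 0.006 SD of the true difference of 0, so the planned analysis is unbiased.

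**The 0-cm floor.** The normal model ignores the floor. An illustrative simulation took 30-70% of subjects at 0 cm at baseline, 30-90% resolution among the rest, no new onset, and final values proportional to baseline. The CI width ratio for adding the own baseline to the body-weight model was 0.28-0.79. These inputs are also assumed, and the proportional structure favours adjustment.

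**Cost if the own baseline explains nothing.** One degree of freedom: the CI is about 0.2% wider at N = 288 and about 1.5% wider at N = 40.

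**Chance imbalance.** The SE of a baseline difference, in SD units, is √(2/144) = 0.118. The probability of a difference of at least 0.2 SD is 2[1 − Φ(0.2 × √72)] = 2[1 − Φ(1.697)] = 0.090 for a given variable. The share passed into the change comparison is |1 − ρk|:
- k = 1, ρ = 0.3 to 0.7: 70% to 30%
- k = 1, ρ = 0.9-0.95: 5-10%
- k = 1.5-2, ρ = 0.3-0.7: 0-55%

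**The case against.** The best case for leaving the plan alone is that this is a matter of efficiency only. The estimates are unbiased, the intervals are valid, protocol and SAP agree with each other, and no decision rests on these variables. All of that stands.

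The size is also uncertain. For cardiothoracic ratio (1-3%) and the three urine and fluid variables (0-7%), the scenarios thought most plausible give little or nothing. The larger figures apply to two of six variables and depend on assumed shrinkage, or on an assumed pattern of zeros for which a linear model is only approximate. This also stands. It limits what can be promised, but the planned model is linear too, and the possible loss is negligible beside the possible gain.

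SAP 7.3 tabulates baseline cardiothoracic ratio, jugular distension and hepatomegaly, and urine volume by category. SAP 8.3.2 adds shift tables and the analysis in subjects with a baseline value. These would make an imbalance or a floor visible; they do not adjust for it. The 9% figure applies to 144 per arm and not to those restricted tables, whose size is unknown.

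Finally, SAP 11 is descriptive, so no covariate was wrongly chosen there. That is fair, and the urine and fluid part is the weaker half of the point. It still reports a between-group difference with a CI, from data that include the baseline.

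**Conclusion.** The point holds as an improvement in precision, not as an error of validity. The secondary ANCOVAs name only baseline body weight, the urine and fluid comparisons name no covariate, and a defined own baseline exists for all six variables.

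The direction of the gain is certain in large samples; its size is not, because ρ and k are unknown. It could be worthwhile for jugular distension and hepatomegaly: 17-35% narrower intervals if k is 0.7-0.85 and ρ is 0.3-0.7, and 8-19% at k = 1 with the same ρ. If those signs prove as stable as assumed for cardiothoracic ratio, the gain is 1-3%. For cardiothoracic ratio itself, and for urine and fluid, it is probably small. The primary conclusion and the 288 subjects are unaffected.

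**What to change.** In SAP 8.3.2, add the baseline value of the variable being analysed as a covariate, including in CT-6.5.2 and CT-6.6.2. Body weight may stay. In SAP 11, report the Day 1 and Day 5 treatment differences in change in urine volume, fluid intake and fluid balance as least-squares mean differences with 95% CIs, from an ANCOVA with treatment and the variable's own baseline. Do this before unblinding, record it in SAP 14, which at present lists no changes, and align protocol 7.4.2.2 and 6.3.

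The cost is small but not nil: a SAP edit, one degree of freedom per model, and a protocol amendment under protocol section 13 for the wording. No new data are needed and no subject is lost, because each baseline is already required to compute the change.
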